Cost-analysis on R-SS compared to laparoscopic multiport hysterectomy in benign gynecology has a knowledge gap. A retrospective study suggests increased cost per case using R-SS compared to laparoscopic multiport hysterectomy (7)(El Hachem et al. 2016). A variety of circumstances influences the analyses such as already established infrastructure for robotic surgery at the hospital, high volume versus low volume robotic centers and experienced robotic teams. Cost-effectiveness analyses are essential in order to provide a responsible utilization of health care resources and includes determination on sick-leave, consultation to healthcare (ex kontakt I amb ell e.l. pga kir.relatedede problemstilling). If out-of-hospital costs are included these may vary between countries; however, the phase between hospital stay and return to work may imply extra cost for the patient, need for reimbursement from health insurances, visits to medical professionals due to related morbidity a.s.o. If rehabilitation with RSS is shorter and includes less extra medical cost and visits the total cost may be less.

Summary:

R-SS hysterectomy is a novel technique, which may be superior to conventional laparoscopic multiport hysterectomy in select patients regarding sick-leave, cosmesis and postoperative pain. We, therefore, aimed at evaluating the learning curve using different robotic equipment (DaVinci Si Multiport surgical system and DaVinci Xi multiport and single site surgical system) in our cohort since 2014 to determine its applicability in our hospital setting. Secondly, we perform a randomized trial to compare R-SS hysterectomy with conventional laparoscopic multiport hysterectomy with regard to outcome postoperative rehabilitation, cosmesis, and the operational cost

Aim of study

Our study aims to evaluate R-SS with respect to:

Primary outcome:

- Length of hospital stay and time to return to daily activities /work
- Cosmesis; pre-and postoperative evaluation
- Postoperative pain (VAS)

Secondary outcome

- Learning curve for robotic-assisted hysterectomy including R-SS hysterectomy
- Patient satisfaction with the cosmesis
- Duration of operation incl. detailed information of time consumption of defined steps at hysterectomy, operation- and console time, blood loss, conversion rates, additional ports, port-site hernias, time at hospital, re-admission
- Cost-effectiveness analysis for the R-SS hysterectomy

Materials and Methods

Study 1:

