The study is scheduled to start May 2018 and compares R-SS hysterectomy to laparoscopic multiport hysterectomy. Procedures are performed by an experienced three-surgeon team. Patients are randomized to either laparoscopic multiport hysterectomy (N=62) or R-SS hysterectomy (N=62) by random numbers in sealed envelopes prepared by a third party. Eligibility criteria are the same as for study 2B (i.e. BMI < 30 kg/m²). Patient's satisfaction with body image and cosmesis is assessed at different time points pre- and postoperatively by means of multidimensional body-self relations questionnaire – appearance evaluation sub-scale and POSAS. Postoperative pain and analgesia use will

be registered as well as secondary outcome parameters as described above. A follow-up at one, three, and six month include self evaluation of the scar and registration of port-site hernias, vaginal dehiscence or other complications (Vercellia et al). Interviews and diaries will include time of return to home and work, daily activities including sexuality

The R-SS hysterectomy is performed using da Vinci, Xi robotic system. One single port, diameter 2 cm is applied at the umbilicus. Applying an additional assistant port is defined as conversion of procedure

The laparoscopic multiport hysterectomy is performed using our standard equipment and 4 trocars, 5 mm each.

Study 3

Socio-economical consequences of R-SS hysterectomy versus conventional laparoscopic hysterectomy

Study details in preparation

Instrumental cost

Hospital stay

Post-hospitalization cost. sick days, extra visits to the out-patient clinic, general practitioner, medical expenses

Sample size calculation was based a PhD- study on fast track hysterectomy, which showed a difference in return to work of 4 days and SD ± 8 . 62 women in each group are needed for a power of 80% (beta=0.2) to replicate this study. To include those not working, we calculated that with an expected VAS of 0.86 ± 0.2 and 62 in each group the sample was sufficient to detect a difference of 0.1 in VAS; still, with a power of 80%. All calculations are based on two-sided testing with alpha = 0.05.

The retrospective study was approved by the Data Authority (no. 1-16-02-913-17). The randomized trial is registered at clinicaltrials.gov (NHS).

Statistics

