For statistical calculations of proportions the χ^2 -test with Yates' correction for discontinuity or the Fisher's Exact-test was used. For continuous variables Student's t-test, Mann-Whitney's U -test, and Wilcoxon's Signed Rank test was used when appropriate.

Questionnaires with partial answers were included in the calculations, if possible. ANOVA and Kruskal Wallis' test was performed between group variables. Post-hoc test with Newman-Keul's test was performed between group pairs, if ANOVA was significant.

Repeated measurements were evaluated with 2-way ANOVA and surgical procedure as group variable with potential confounding variables like age, BMI, surgeon, and additional surgery added. The distribution of BMI, age, blood loss, split times during operation, hospital stay and time of return to daily activities and work were evaluated by means of Kaplan-Meyer analysis. The level of significance was a two-sided $p < 0.05$. Logistics regression analysis was performed with surgical procedure as dependent variable and the various split times, surgeon, age, BMI, parity, as independent variables. Learning curves were established for each individual surgeon, surgical procedures, and combined

monitored over time of the studies. Data are given as mean \pm SD if following Gaussian distribution and median (minimum, maximum) if non-Gaussian distributed. IBM SPSS Statistics 20 was used as the statistical software

Research plan

Study 1; jan 2017-june 2018

Study 2; may. 2018-jan. 2020

Study 3; 2020-2021

Responsibility:

[name] [name], [name]. Department of Gynecology and Obstetrics, Herning Hospital, Principal data supervisor and investigator for clinicaltrials.gov
[name], Ph.D. Department of Gynecology and Obstetrics, Herning Hospital

References

El Hachem, L., et al. (2016). "Robotic Single-Site and Conventional Laparoscopic Surgery in Gynecology: Clinical Outcomes and Cost Analysis of a Matched Case-Control Study." *J Minim Invasive Gynecol* **23**(5): 760-768.

Golkar, F. C., et al. (2012). "Patients' perceptions of laparoendoscopic single-site surgery: the cosmetic effect." *Am J Surg* **204**(5): 751-761.

Sandberg, E. M., et al. (2017). "Laparoendoscopic single-site surgery versus conventional laparoscopy for hysterectomy: a systematic review and meta-analysis." *Arch Gynecol Obstet* **295**(5): 1089-1103.

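### The 80% power claimed for return to work needs a return-to-work time from every randomised woman, yet the same 62 per arm include women who do not work

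*Protocol*

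**What the plan says.** The sample size paragraph stands at the end of Study 3 in the protocol. It takes from an earlier fast-track hysterectomy study "a difference in return to work of 4 days and SD ± 8" and concludes that "62 women in each group are needed for a power of 80% (beta=0.2) to replicate this study". The test is two-sided: "All calculations are based on two-sided testing with alpha = 0.05".

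The same paragraph then turns to women without a job: "To include those not working, we calculated that with an expected VAS of 0.86 ± 0.2 and 62 in each group the sample was sufficient". The target there is a VAS difference of 0.1, again with 80% power.

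Study 2 randomises 62 women to each arm. The eligibility criteria it takes over from Study 1 contain no employment requirement.

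Under Aim of study, one of the primary outcomes is "Length of hospital stay and time to return to daily activities /work". The Statistics section says that "hospital stay and time of return to daily activities and work were evaluated by means of Kaplan-Meyer analysis".

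**The concern.** The number said to be needed for the return-to-work comparison is also the total number randomised. The protocol itself says that this total includes women who cannot contribute a return-to-work time. So the 80% holds only if every woman is in work and gives a date, which the paragraph's own next sentence rules out as the intended population.

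Return to work is the outcome on which the trial was sized, and it is part of a listed primary outcome. If its true power is well below 80%, a null result could be read as evidence of equal recovery when the trial had too few informative women to show a difference.

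**Working it through.** **Inputs** (all from the sample size paragraph, except the number randomised, which is from Study 2): difference 4 days; SD 8 days; two-sided alpha 0.05; power 80%; 62 randomised per arm.

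**1. The plan's own figure.** The standardised difference is 4/8 = 0.5.

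- Normal approximation: n per arm = 2 × (1.960 + 0.842)² × (8/4)² = 62.8, so 63.
- t-test (noncentral t): 63.8, so 64.
- Power with 62 per arm: 79.5% (normal), 78.9% (t-test).

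The stated 62 is therefore reproduced to within rounding. It is not a miscalculation, but it leaves no margin.

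**2. The VAS calculation.** 0.1/0.2 = 0.5, the same standardised difference. With 62 per arm, power is again 79.5% (normal) or 78.9% (t-test). This reproduces too. It is a statement about pain, and it has no spare margin either.

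**3. Power for return to work when some women have no return-to-work time.** The protocol gives no working share, so thresholds come first, because they need no assumption about it. They suppose equal losses in the two arms (t-test, two-sided 0.05, standardised difference 0.5):

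- Power equals 75% at 56.5 women per arm. With 6 of 62 missing, 56 remain and power is 74.6%.
- Power equals 70% at 50.4 women per arm. With 12 of 62 missing, 50 remain and power is 69.7%.

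**4. The same as an assumed range.** The shares below are illustrations, not figures from the protocol.

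| Assumed share with a return-to-work time | Women per arm | Power for 4 days | Difference detectable with 80% power |
|---|---|---|---|
| 100% | 62.0 | 78.9% | 4.06 days |
| 95% | 58.9 | 76.8% | 4.16 days |
| 90% | 55.8 | 74.5% | 4.28 days |
| 80% | 49.6 | 69.3% | 4.55 days |
| 70% | 43.4 | 63.4% | 4.87 days |

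**5. What keeping 80% would take.** Divide the 63 to 64 women required by the share with a return-to-work time: 70 to 72 per arm at 90%, 79 to 80 at 80%, and 90 to 92 at 70%.

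**The case against.** The strongest reply is that the listed primary outcome covers daily activities as well as work, and that diaries and interviews collect both. A woman without a job can give a daily-activities date, so she is not lost to that outcome. This is true, and it limits the point to the work component. It does not rescue the power claim: the 4 days and SD 8 are given for return to work only, and the protocol gives no difference or SD for daily activities or for the two combined.

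A second reply is that the protocol deals openly with women not working, by powering pain for everyone, and never says that this restores power for return to work. That is a fair reading. But the 80% for return to work is still stated without qualification, and the VAS calculation adds no return-to-work data.

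A third is that Kaplan-Meier analysis copes with incomplete follow-up. It does so for an employed woman lost early, who can be censored, so the t-test figures somewhat overstate the loss from such women. A woman without a job is never at risk of returning to work, and censoring her adds no information.

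Two further objections stand in full. The difference between 62 and 63 to 64 is rounding and should not be called an error. The size of the shortfall also cannot be found from the protocol, because it gives neither a working share nor a rate of missing dates.

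**Conclusion.** The point holds. The design does not deliver the 80% power stated for return to work. On the protocol's own inputs, t-test power is at most 78.9%, and each randomised woman without a return-to-work time lowers it. It falls below 75% when 6 of 62 per arm lack one and below 70% when 12 do. Over an assumed 70% to 95% with a date, it runs from 63.4% to 76.8%.

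These figures rest on the stated 4 days and SD 8, on a t-test and on equal losses in the arms. The direction is certain; the size depends on a working share that the protocol does not give. Power for VAS pain is not affected by women being out of work. The paragraph should be corrected, but nothing here calls for a change in design.

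**What to change.** Replace the sample size paragraph with wording along these lines:

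> With 62 women per group, power is about 79% (two-sided alpha 0.05) for a 4-day difference in return to work (SD 8) only if all 62 are in work and supply a date. With the expected [n] per group in work at baseline and followed, power is [x]% and the difference detectable with 80% power is [y] days (for example, with 50 per group: about 70% and 4.5 days). Return to work is compared among women employed at baseline. Separately, for pain in all women, 62 per group give about 79% power for a VAS difference of 0.1 (SD 0.2).

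The sponsor fills the blanks from its own expectation of how many women will be in work. Recording employment before randomisation keeps the work comparison a randomised one. The combined primary outcome can stay as listed; the new sentence only says to whom the return-to-work power applies.

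The cost is one reworded paragraph and one baseline item. No extra women and no new endpoint are needed. What is given up is the 80% figure: the stated power for return to work becomes less favourable. If the sponsor wants to keep 80%, the price is the larger enrolment shown in step 5 of the working.

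### Yates-corrected chi-square or Fisher's exact test for every proportion is valid but more conservative than needed at 62 v 62; Boschloo's test keeps the 5% limit and gains modest power (minor, secondary outcomes)

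*Protocol*

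**What the plan says.** The Statistics section names two tests for proportions and no others: chi-square "with Yates' correction for discontinuity or the Fisher's Exact-test was used". The same section sets the threshold: "The level of significance was a two-sided" p below 0.05. The sample-size paragraph (printed under Study 3) uses the same level: "All calculations are based on two-sided testing with alpha = 0.05".

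Study 2 fixes the arms: "laparoscopic multiport hysterectomy (N=62) or R-SS hysterectomy (N=62) by random numbers in sealed envelopes".

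The proportions concerned are secondary or follow-up items. The secondary outcomes under Aim of study include "blood loss, conversion rates, additional ports, port-site hernias, time at hospital, re-admission", of which conversion, additional ports, hernia and re-admission are yes/no outcomes. Follow-up in Study 2 includes "registration of port-site hernias, vaginal dehiscence or other complications". The protocol gives no event rate, power target or safety hypothesis for any of these.

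**The concern.** Yates' correction and Fisher's conditioning on the margins both make a 2×2 comparison conservative, most of all when events are few. The randomised trial has two arms of fixed size, so an unconditional exact test is available that respects the same 5% limit and gives up less power.

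The outcomes affected are those on which a new technique might turn out worse: conversion, hernia, dehiscence, re-admission and other complications. An avoidably strict test makes a non-significant result on them somewhat more likely even when the arms truly differ. The primary outcomes are not touched.

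**Working it through.** **Inputs.** 62 per arm (Study 2); two-sided 0.05 and the two tests (Statistics). The only comparative event rates in the document are the transfusion rates of 4.0% and 7.9% in the background section on multi-port and single-site laparoscopy. All other event rates below are assumptions. All 62 per arm are taken as analysed.

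**The plan's own figure.** The planning input is that an earlier study "showed a difference in return to work of 4 days and SD ± 8". Then n = 2 × (1.96 + 0.8416)² × (8/4)² = 2 × 7.849 × 4 = 62.8, so 63 per arm. Power at 62 is 79.5% by the normal approximation. The stated 62 is reproduced within tolerance. It rests on continuous outcomes only, so no proportion entered the sizing.

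**Method.** List all 63 × 63 possible results (x events in one arm, y in the other) and mark the set R in which a test rejects. With b(x; 62, p) the binomial probability:

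- error rate at event rate p = sum over R of b(x; 62, p) × b(y; 62, p)
- power at p₁ v p₂ = sum over R of b(x; 62, p₁) × b(y; 62, p₂)

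Boschloo's test uses Fisher's p-value as its statistic. Its cut-off is the largest Fisher p whose error rate, maximised over p, is at most 5%. At 62 v 62 that cut-off is 0.069.

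**Error rate.** Yates and Fisher reject the same tables at 62 v 62, so choosing between them makes no difference.

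| Event rate in both arms | Yates or Fisher | Boschloo |
|---|---|---|
| 1% | 0.00% | 0.04% |
| 2% | 0.09% | 0.5% |
| 3% | 0.35% | 1.3% |
| 5% | 1.1% | 2.8% |
| 10% | 2.3% | 3.4% |
| Maximum over all rates | 3.84% | 4.99% |

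**Power.**

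| True rates | Yates or Fisher | Boschloo |
|---|---|---|
| 2% v 10% | 29% | 41% |
| 2% v 12% | 45% | 56% |
| 3% v 15% | 54% | 63% |
| 5% v 20% | 65% | 70% |
| 10% v 25% | 51% | 57% |
| 5% v 10% | 9% | 14% |
| 4.0% v 7.9% | 6% | 11% |
| 2% v 5% | 3% | 7% |

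**One table by hand.** Take 5 events against 0. Fisher's two-sided p = 2 × (62 × 61 × 60 × 59 × 58) / (124 × 123 × 122 × 121 × 120) = 2 × 0.02874 = 0.057, not significant. Yates: 124 × (310 − 62)² / (62 × 62 × 5 × 119) = 3.33, below 3.84, also not significant. Since 0.057 is below 0.069, Boschloo rejects. The same happens at 1 v 7 (Fisher p = 0.062). Against 0, 1, 2 or 3 events, Fisher needs 6, 8, 10 or 11 in the other arm; Boschloo needs 5, 7, 9 or 11.

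**What sample size contributes.** For 4.0% v 7.9% at 80% power, n = [1.96 × √(2 × 0.0595 × 0.9405) + 0.8416 × √(0.04 × 0.96 + 0.079 × 0.921)]² / 0.039² = (0.6557 + 0.2806)² / 0.001521, about 577 per arm. No test makes up the gap between 62 and 577.

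**The case against.** The strongest reply is that nothing here is wrong. A threshold of p below 0.05 is a ceiling, not a promise that the realised error rate equals 5%, and both named tests stay under it. They are standard, the outcomes are secondary, and the practical difference is often a single event. All of this stands, and it is why the point is minor.

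A reader might go further and infer that the protocol misstates its error rate, or that the choice of test leaves the trial blind to harms. The documents support neither reading. Discrete counts and the sample size are the main limits for rare events: Boschloo's own error rate is only 1.3% to 2.8% at event rates of 3% to 5%, and differences such as 2% v 5% are missed by every test. Nor does the protocol plan to read a non-significant comparison as evidence of safety. It gives no rates for hernia, dehiscence, re-admission or conversion, and conversion in the robotic arm includes any added assistant port, so it need not be rare. The 4.0% v 7.9% figures favour the single-port arm and come from a laparoscopic trial, so they are not evidence of harm.

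What the reply does not remove is that, for two fixed arms and the same 5% limit, Boschloo's test rejects every table that Fisher's does and some more. Its power is therefore never lower.

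**Conclusion.** The point holds as a cheap improvement, not as an error in the plan. At 62 v 62 the named tests run at about 0.4% to 2.3% for event rates of 3% to 10%, and never above 3.8%. Boschloo's test remains within 5% and gains about 5 to 12 points of power for differences of 10 to 15 percentage points, often by shifting the boundary by one event. For small differences in rare harms, power stays very low under either test.

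The figures assume 62 analysed per arm and the event rates shown; losses to follow-up would change them somewhat. The priority is minor and limited to secondary proportions in the randomised comparison.

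**What to change.** In the Statistics section, replace the sentence on proportions, for the randomised comparison, by:

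> Two-by-two proportions between the randomised arms are compared by Boschloo's unconditional exact test at two-sided 5%, and reported with the risk difference and its 95% score confidence interval; a non-significant result is not read as absence of a difference.

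The interval matters at least as much as the test, because it shows how large a difference remains compatible with the data when few events occur.

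The cost is one sentence, with no extra patients or data. Boschloo's test may need free software outside SPSS, the package that the protocol names. The uncorrected chi-square multiplied by (N − 1)/N would be easier to run in SPSS, but it is not recommended as a substitute: its error rate at 62 v 62 can reach 5.9%, above the protocol's own limit.

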Detailed learning curves for robotic surgery- single site and multiport hysterectomy – a prospective, controlled study. A retrospective study of all robotic hysterectomy since 2014

The prospective controlled study compares R-SSH with robotic multiport hysterectomy (the controls) and will be performed at the Department of Gynecology, Herning Hospital, between September 2016 to end of December 2017. Sample size is estimated based on recommendations from the literature (8)(Cala V. et al. 2012). The study consists of two sub-studies (A and B). Each of the two sub-studies includes 40 procedures performed by two experienced laparoscopists with 20 procedures each.

A: Determination of learning curve for two similar experienced surgeons, for 40 robotic *multiport* hysterectomies – 20 hysterectomies per surgeon.

Inclusion criteria for the learning curve studies are hysterectomy on benign indication, ASA group 1 or 2, BMI (body mass in kg/heights in metres²) less than 35 kg/m² (for R-SS hysterectomy less than 30), uterine size less than 300 g estimated by ultrasound, using Ferraris formula.

Exclusion criteria are risk of adhesions, prior extensive abdominal surgery and prior midline incision, cutis laxa of abdomen surgery, endometriosis, and more than 1 cesarean section.

The procedure is video recorded and peri-and postoperative data are collected prospectively. Various steps during the procedure are determined such as various split time measurements like docking time, console time, vaginal cuff suturing, incision start, skin-to-skin and closure time. Uterine size and blood loss, as well as patient demographic data are registered.

B. The on-going study estimates the learning curve for *R-SS* hysterectomy. In- and exclusion criteria as for Study 1 except for inclusion criteria of BMI less than 30 kg/m²

C. Further, a retrospective cohort from the first robotic hysterectomies in 2014 until recently will be evaluated. The surgeries in the prospective studies are performed using the Da Vinci Xi surgical system and in the retrospective study using the Da Vinci Si Multiport system. Due to its design only crude incidences on perioperative variables will be evaluated.

Study 2

Robotic single-site hysterectomy compared to laparoscopic multiport hysterectomy – a prospective randomized controlled study; cosmetic satisfaction and surgical outcome.

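### Newman-Keuls is fixed as the post-hoc test without naming the groups; with four or more groups it does not in general hold a 5% family-wise error

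*Protocol*

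**What the plan says.** The Statistics section of the Protocol gives a general multi-group analysis: "ANOVA and Kruskal Wallis' test was performed between group variables". It then fixes the follow-up: "Post-hoc test with Newman-Keul's test was performed between group pairs, if ANOVA was significant". The significance level is two-sided 0.05, and no other multiplicity control is named for these comparisons. Neither the grouping factor nor the number of groups is given.

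Three other statements bear on how many groups there could be:

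- Study 1 (Materials and Methods): "Each of the two sub-studies includes 40 procedures performed by two experienced laparoscopists with 20 procedures each". One sub-study is robotic multiport and the other is robotic single-site.
- Study 2: "Procedures are performed by an experienced three-surgeon team". There are two randomised arms of 62.
- Statistics, on the learning curves: "Learning curves were established for each individual surgeon, surgical procedures, and combined".

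**The concern.** Newman-Keuls tests the range of each ordered subset of means against a critical value that depends on the size of that subset. Two adjacent means are therefore judged as if they were the only two in the analysis. This protects the whole set of comparisons when all means are equal, or when there are only three groups. From four groups on, the means can form two or more separate clusters of truly equal groups. Each cluster is then tested at about 5% and the errors add up. The preceding ANOVA gives no protection in that case, because the real difference between clusters makes it significant.

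Study 1 could produce this pattern. The Protocol describes its surgeons as alike: "Determination of learning curve for two similar experienced surgeons, for 40 robotic *multiport* hysterectomies – 20 hysterectomies per surgeon". If they do perform alike and the techniques differ, the four surgeon-by-technique cells form two equal pairs separated by technique. A false difference between surgeons within a technique, for example in a split time, would then be declared more often than the reader of a 5% level expects. Split times and learning curves are secondary outcomes of the project.

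**Working it through.** **The plan's own figure.** The Protocol gives no error rate for the post-hoc test. Its one reproducible figure is the sample size of the randomised trial: a difference of 4 days, SD 8, 80% power, two-sided 0.05.

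n per group = 2 × [SD × (z₀.₉₇₅ + z₀.₈₀) / difference]² = 2 × [8 × (1.960 + 0.842) / 4]² = 62.8

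This agrees with the stated 62, at which power is 79.5%. It rests on two arms and does not involve the post-hoc test.

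**Counting groups.**

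- Study 1: 2 techniques × 2 surgeons = 4 cells of 20.
- Study 2: 2 arms × 3 surgeons = up to 6 cells. If the 124 women were shared evenly, that is 124 / 6 = 20.7 per cell. The even split is an assumption.
- Technique alone: 2 levels within either study, and 3 if the studies are pooled (robotic multiport, robotic single-site, laparoscopic multiport).
- Surgeon alone: 2 in Study 1, 3 in Study 2.

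**Simulation.** Data were normal with common SD, 20 per group, and 200,000 replicates per pattern. The steps were:

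1. Overall F test at 5%, with k − 1 and k(20 − 1) degrees of freedom. Continue only if it is significant, as the Protocol requires.
2. Newman-Keuls: order the means. For a range spanning r means, reject if (largest − smallest) / √(s²/20) exceeds the 5% studentized-range value for r means, and only if every wider range containing it was rejected.
3. Tukey's HSD, for comparison: the same statistic and the same F gate, but always with the critical value for all k means.
4. Family-wise error: the share of replicates with at least one rejection between truly equal groups.

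| Pattern | Newman-Keuls | Tukey's HSD |
|---|---|---|
| 3 groups, all equal | 4.5% | 4.5% |
| 3 groups, two equal, one far away | 5.0% | 1.9% |
| 4 cells, all equal | 4.3% | 4.3% |
| 4 cells, three equal, one far away | 5.0% | 2.8% |
| 4 cells, two equal pairs 0.5 SD apart | 6.1% | 2.1% |
| 4 cells, two equal pairs 1 SD apart | 9.5% | 2.1% |
| 4 cells, two equal pairs 1.5 SD apart | 9.7% | 2.1% |
| 4 cells, two equal pairs far apart (5 SD) | 9.7% | 2.1% |
| 6 cells, all equal | 3.8% | 3.8% |
| 6 cells, two equal triples far apart | 9.7% | 2.5% |
| 6 cells, three equal pairs far apart | 14.1% | 1.4% |

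The Monte Carlo standard error at 10% is √(0.10 × 0.90 / 200,000) = 0.07 percentage points.

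**Check against theory.** With well separated pairs, each null pair is tested at about 5%, nearly independently. Two pairs give 1 − 0.95² = 9.75% and three give 1 − 0.95³ = 14.3%, which matches 9.7% and 14.1%.

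**The case against.** The strongest objection is that the Protocol never says it compares surgeon-by-technique cells. Where the Statistics section does name a group variable, in the repeated-measures ANOVA, it is the surgical procedure, and surgeon appears among the potential confounders. Procedure has two levels in each study and three if pooled. Surgeon alone gives two or three. With three groups Newman-Keuls holds its level. The retrospective cohort might add a group, but Study 1 limits it to crude incidences. The sentence on learning curves concerns curves, not post-hoc tests, and does not clearly cross surgeon with procedure. All of this stands, and it makes the point conditional.

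It does not remove the point. The grouping for the general ANOVA is left open, and a post-hoc test has a purpose only with three or more groups. Within prospective Study 1 neither factor alone has more than two levels, so the direct way to need the test is the four cells.

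Two further objections also stand:

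- The excess depends on the pattern. At 0.5 SD, the standardised effect behind the sample size (4 / 8, for a different outcome), it is about one percentage point.
- The Protocol states a significance level and promises no family-wise 5%. Still, limiting error across a set of pairs is the usual reason to name a multiple-comparison procedure.

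A reader might also infer that Newman-Keuls is misapplied after Kruskal-Wallis, which is named in the same place. The text does not support that, because it makes Newman-Keuls conditional on a significant ANOVA.

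**Conclusion.** The point holds as a minor, conditional one. The Protocol fixes a pairwise procedure that is sound for three groups but not in general for four or more, and it does not say how many groups there are. If the four Study 1 cells of 20 are compared, the family-wise error lies between about 4% (all equal) and nearly 10% (two equal pairs 1 SD or more apart), with 6% at 0.5 SD. The figures assume normal data with equal variances, 20 per cell, and the ANOVA gate as written.

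Two stronger readings go beyond the documents:

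- A reader might conclude that the trial will run at a 10% to 14% error rate. That requires the cells to be compared, which is not stated, and it takes only the least favourable patterns. The 14% also needs six cells in three distinct equal pairs, and Study 2 does not say that each surgeon operates in both arms or is compared by arm.
- A reader might think the randomised result is affected. It is not: two arms call for no post-hoc test, so the comparison between arms and the 62 per group stand as they are.

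**What to change.** Make two changes to the Statistics section:

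- Name the groups that enter each ANOVA: technique, surgeon, or surgeon-by-technique cells.
- Replace Newman-Keuls by a procedure with strong family-wise control, such as Tukey's HSD. In the patterns checked its error was between 1.4% and 4.5%.

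Changing the method alone would leave unclear which comparisons are meant, so both parts are needed. Together they are an edit of a line or two, with no effect on data collection or sample size. The cost is slightly lower power for the secondary pairwise comparisons, because every pair is held to the critical value for the full set of groups.
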